2. SUMMARY OF KEY PROTOCOL INFORMATION

2.1. Changes to the Protocol Defined Statistical Analysis Plan

Any changes from the originally planned statistical analysis specified in the protocol are outlined in [Table 1](#).

Table 1 Changes to Protocol Defined Analysis Plan

Protocol	Reporting & Analysis Plan	
Statistical Analysis Plan	Statistical Analysis Plan	Rationale for Changes

 For Hgb Day 1 measurement using central lab Quest will serve as the baseline value. (Section 7.3) 	
 For Hgb the average of Hgb measured by the central lab, Quest, at Week -2 and Day 1 visits will serve as the baseline value. 	
 Average of Hgb measured by the central lab, Quest, at Week -2 and Day 1 visits will reflect the overall pre-treatment stable Hgb level.

2.2. Study Objective(s) and Endpoint(s)

Objectives	Endpoints
Primary Objectives	Primary Endpoints

 Characterize the dose-response relationship between GSK1278863 administered three-times weekly and Hgb at Day 29 	
 Hgb change from baseline at Day 29
Secondary Objectives	Secondary Endpoints

 Characterize the pharmacodynamic (PD) effect of GSK1278863 dose regimens on EPO, vascular endothelial growth factor (VEGF), hepcidin and red blood cells 	
 Maximum observed change from baseline in EPO Maximum observed % change from baseline in VEGF Change from baseline in hepcidin at Day 29 Change from baseline in hematocrit, red blood cell (RBC) count, reticulocyte count and reticulocyte Hgb (CHr) at Day 29

 Characterize the steady-state PK of GSK1278863 and major metabolites 	
 Descriptive PK summaries of GSK1278863 and major metabolites

 Assess the safety and tolerability of GSK1278863 with three-times weekly administration for 29 days 	
 Incidence and severity of AEs and SAEs Reasons for discontinuation of investigational product Discontinuation for safety-related reasons, e.g., pre-specified stopping criteria or AE Absolute values and changes from baseline over time in laboratory parameters, ECGs and vital signs.
Exploratory Objectives	Exploratory Endpoints

 Evaluate exposure-response relationships between GSK1278863 and PD endpoints 	
 Further models (as appropriate) to describe the GSK1278863 exposure (PK or dose)-response relationship with PD endpoints

2.3. Study Design

Overview of Study Design and Key Features	

Treatment Period Day 1 - 29
 
10 mg Three-times weekly
 
15 mg Three-times weekly
 
25 mg Three-times weekly
 
30 mg Three-times weekly
 
Placebo
 
Screening Day -28 to Day -1
 
Follow-Up Day 43 (± 3 Days)
 
↑ Randomization (1:1:1:1:1)
	
Design Features	
 • A randomized, double-blinded, dose-ranging, placebo-controlled, parallel group study. • There is a 28-day Screening period, a 29-day Treatment period, and a Follow-up visit 14 ±3 days after completing treatment.
Dosing	
 • Subjects who meet eligibility criteria will be randomized and begin dosing on Day 1. Subjects will discontinue their current ESA therapy and will be randomized to receive one of four three-times weekly doses (10 mg, 15 mg, 25 mg, or 30 mg of GSK1278863), or placebo on a dialysis day. 
 • This should be timed such that randomization (Day 1) occurs on the date that would have been the next scheduled dose of ESA (or as close as practicable). • For subjects with a three-times weekly dialysis schedule, Day 1 must not occur on the first dialysis session of the week (e.g., if Monday-Wednesday-Friday schedule, the study visit cannot be on Monday). • For subjects with a four- to five-times weekly dialysis schedule, Day 1 can be on any hemodialysis session of the week. • The treatment period will be for a total of 29 days.
Treatment Assignment	
 • Approximately 200 subjects will be screened to achieve approximately 90 randomized and 75 evaluable subjects, with approximately 15 evaluable subjects per treatment group. • Subjects will be randomized 1:1:1:1:1 to receive one of four three-times weekly doses (10 mg, 15 mg, 25 mg, 30 mg), or placebo on a dialysis day

Overview of Study Design and Key Features	
	
 • Randomization schedule will be computer generated by PPD using the randomization system Prism. • Subjects will be stratified by prior ESA dose based on the average weekly (for epoetins or darbepoetin) or monthly (for methoxy PEG-epoetin beta) dosing during the 12 weeks prior to randomization (Day 1). • Central randomization and PPD's Interactive Voice/Web Response System (IVWRS) will be used for treatment allocation.
Interim Analysis	
 • No interim analysis is planned.

2.4. Statistical Hypotheses

No formal hypothesis will be tested. This study is designed to estimate the relationship between three-times weekly doses of GSK1278863 and Hgb response after 29 days of treatment in hemodialysis-dependent subjects with anemia associated with chronic kidney disease who are switched from a stable dose of an erythropoiesis-stimulating agent. To achieve this, a model-based dose-response analysis is planned with the primary endpoint of change in Hgb from baseline at Day 29. It is anticipated that the data and the estimated parameters generated from this model will enable conversion of QD starting and maintenance dose regimens to three-times weekly doses/regimens.

3. PLANNED ANALYSES

3.1. Interim Analyses

No interim analysis is planned

3.2. Final Analyses

The final planned primary analyses will be performed after the completion of the following sequential steps:

1. All subjects have completed or withdrawn from the study as defined in the protocol
2. All required database cleaning activities have been completed and final database release and database freeze has been declared by both PPD and GSK Data Management.
3. All criteria for unblinding the randomization codes have been met.
4. Randomization codes have been distributed according to GSK and PPD procedures.

The final analyses with the exception of the dose-response analysis will be performed by PPD. All dose-response analyses as described in Section 7.1.2 will be carried out by GSK.

4. ANALYSIS POPULATIONS

Population	Definition / Criteria	Analyses Evaluated
All Screened	
 Comprise all subjects who consented to participate in the clinical trial and were screened. 	
 Summarize the screen failure subjects
All Randomized	
 Comprise all randomized subjects regardless of whether they took study drug. This population will be based on the treatment to which the subject was randomized. Any subject who received a treatment randomization number will be considered to have been randomized. 	
 Describe the breakdown of Study Populations Study Population Selected listings
Safety	
 Comprise all subjects who received at least one dose of study treatment. This population will be based on the treatment and the actual dose the subject received. 
Note: (1) If a subject randomized to the placebo arm, temporarily received daprodustat by mistake during the study, then the subject would be included in the corresponding daprodustat arm in the Safety population. (2) If a subject randomized to one of the daprodustat arms, temporarily received placebo by mistake during study, then the subject would remain in the randomized daprodustat arm in the Safety population.(3) If a subject randomized to one of the daprodustat arms, received a wrong dose of daprodustat by mistake throughout the study, then the subject will be included in the daprodustat arm in the Safety population based on the actual daprodustat dose received.(4) If a subject randomized to one of the daprodustat arms, temporarily received wrong dose of daprodustat by mistake during study, then the subject would be included in the daprodustat arm from which the subject received >50% of the study medication.
	
 Study Population Safety and tolerability
Intent-To-Treat	
 Comprise all randomized subjects who received at least one dose of study treatment, had a baseline and at least one corresponding on treatment assessment, including Hgb (Quest or HemoCue) This population will be based on the treatment to which the subject was randomized. 	
 Efficacy
Per-Protocol	
 Comprise all Intent-To-Treat subjects who 	
 Efficacy

Population	Definition / Criteria	Analyses Evaluated
	
were not major protocol violators with regards to inclusion/exclusion criteria, investigational product compliance and concomitant medication instructions.
 
 Protocol deviations that would exclude subjects from the PP population are defined in Section 4.1 (Protocol Deviations) and Appendix 1 (Protocol Deviation Management and Definition for Per-Protocol Population). The Per-Protocol population will be used for sensitivity analyses. The Per-Protocol population will not be analyzed if this population comprises more than 80% of the Intent-To-Treat population. 	
Completer	
 Comprise all Intent-To-Treat subjects who fully completed the Day 29 study assessments without prematurely discontinuing study drug. The Completer Population will be used for sensitivity analyses. 	
 Efficacy
Pharmacokinetic Population	
 Comprises all subjects from whom a pharmacokinetic sample has been obtained and analyzed. 	
 PK

NOTES :

- Please refer to [Appendix 14](#): List of Data Displays which details the population to be used for each displays being generated.

4.1. Protocol Deviations

- Important/significant protocol deviations (including deviations related to study inclusion/exclusion criteria, conduct of the trial, patient management or patient assessment) will be summarised and listed.
- Important/significant deviations which result in exclusion from the analysis population will also be summarised and listed. (Please refer to [Appendix 1](#): Protocol Deviation Management and Definitions for Per Protocol Population).

All protocol deviations, including significant protocol deviation, will be tracked in PPD CTMS (Clinical Trial Management System), and will be reviewed by PPD and GSK study team throughout the conduct of the study in accordance with PPD's Study Deviation Rules Document.

- Data will be reviewed prior to unblinding and freezing the database to ensure all important deviations and deviations which may lead to exclusion from the analysis are captured and categorised on the protocol deviations dataset.

- This dataset will be the basis for the summaries and listings of protocol deviations.
- A separate summary and listing of all inclusion/exclusion criteria deviations will also be provided. This summary will be based on data as recorded on the inclusion/exclusion page of the eCRF.

5. CONSIDERATIONS FOR DATA ANALYSES AND DATA HANDLING CONVENTIONS

- There are planned examination of covariates and subgroups.
- There are no planned adjustments made for multiple centres in this study.
- There are no planned adjustments for multiple comparisons or multiplicity.

Table 2 provides an overview of appendices within the RAP for outlining general considerations for data analyses and data handling conventions.

Table 2 Overview of Appendices

Section	Component
Section 11.1	Appendix 1 : Protocol Deviation Management and Definitions for Per Protocol Population
Section 11.2	Appendix 2 : Time & Events
Section 11.3	Appendix 3 : Assessment Windows
Section 11.4	Appendix 4 : Treatment States and Study Phases
Section 11.5	Appendix 5 : Data Display Standards & Handling Conventions
Section 11.6	Appendix 6 : Derived and Transformed Data
Section 11.7	Appendix 7 : Premature Withdrawals & Handling of Missing Data
Section 11.8	Appendix 8 : Values of Potential Clinical Importance
Section 11.9	Appendix 9 : Multicenter Studies
Section 11.10	Appendix 10 : Examination of Covariates and Subgroups
Section 11.11	Appendix 11 : Multiple Comparisons & Multiplicity
Section 11.12	Appendix 12 : Model Checking and Diagnostics for Statistical Analyses.
Section 11.13.	Appendix 13 : Abbreviations & Trade Marks
Section 11.14	Appendix 14 : List of Data Displays
Section 11.15	Appendix 15 : Example Mock Shells for Data Displays

6. STUDY POPULATION ANALYSES

6.1. Overview of Planned Analyses

The study population analyses will be based on either the Safety population, the ITT population or the All Randomized population, unless otherwise specified. All summary tables will include a Total column and a Dapro Total column, unless otherwise specified.

[Table 3](#) provides an overview of the planned study population analyses, with full details of data displays being presented in [Appendix 14](#): List of Data Displays.

Table 3 Overview of Planned Study Population Analyses

Display Type	Data Displays Generated		
	Table	Figure	Listing
Subject Disposition			
Subject Disposition	Y		
Reasons for Screening Failure	Y		Y
Study Treatment Discontinuation	Y		Y
Reasons for Study Withdrawal			Y
Subjects for Whom the Treatment Blind was Broken			Y
Randomized and Actual Treatment Assignment			Y
Subjects at Each Visit	Y		
Protocol Deviations			
Important Protocol Deviations	Y		Y
Deviations Leading to Exclusions from Per Protocol Population	Y		[1]
Subjects with Inclusion/Exclusion Criteria Deviations	Y		Y
Populations Analyzed			
Study Populations	Y		Y
Number of Subjects by Center	Y		
Subjects Excluded from Any Population			Y
Demography			
Demographic and Other Baseline Characteristics	Y		Y
Race & Racial Combinations	Y		Y ^[2]
Summary of Race and Racial Combination Details	Y		Y ^[2]
Medical Condition & Concomitant Medications			
Medical Conditions (Current/Past)	Y		Y
Concomitant Medication	Y		Y
Relationship Between ATC Level 1, Ingredients And Verbatim Text			Y
Cardiovascular Risk Assessment			Y
Family History of Cardiovascular Risk	Y		

Display Type	Data Displays Generated		
	Table	Figure	Listing
Substance Use History	Y		Y
Baseline Hemodialysis	Y		Y
Prior Erythropoiesis-Stimulating Agents	Y	Y	Y
Erythropoiesis Stimulating Agents Medications			Y
Standardized Prior Recombinant Human Erythropoietin Dose		Y	
Concomitant Erythropoiesis-Stimulating Agents	Y		
Pre-therapy Average Iron Dose	Y		
On-therapy Average Iron Dose	Y		
Subjects Using IV Iron Dose Between Study Treatment Start and Final Visit	Y		
Iron Therapy			Y
Blood Products	Y		Y
Exposure and Treatment Compliance			
Study Medication Overall Compliance	Y		Y
Extent of Exposure to Study Treatment	Y		Y

NOTES :

- Subjects with protocol deviations leading to exclusions from Per Protocol population will be listed in Listing of Subjects Excluded from Any Populations
- Listing of race will be generated, which includes both "Race and Racial Combinations" and "Race and Racial Combination Details"

6.2. Display Details**6.2.1. Subject Disposition**

The number of subjects who completed the study for purpose of the disposition table will consist of all randomized subjects who, as documented in the eCRF, have completed all study visits, including the follow-up visit.

Reasons for withdrawal from study and study treatment will be summarized for each treatment group and overall. A by-subject listing of reasons for study withdrawal and a by-subject listing of reasons for study treatment discontinuation will be produced.

The number and percentage of subjects who failed screening and were therefore not entered into the study, overall and by reason, will be summarized. A listing of the screen failure record for all subjects who failed screening, including the reasons for screen failure will be produced.

The number and percentage of subjects at each visit will be summarized for each treatment group and overall.

A listing of subjects for whom the treatment blind was broken and a listing of randomized and actual treatment assignment will be produced.

6.2.2. Protocol Deviations

The number and percentage of subjects who had important/significant protocol deviations defined in Section 11.1.1 will be summarized overall and by treatment group. (Note: Given that different terminologies have been used by GSK and PPD, the terms “important protocol deviation” and “significant protocol deviation” will be used interchangeably throughout the RAP.)

Protocol deviations leading to exclusion from Per Protocol population will be summarized overall and by treatment group. (See Section 11.1.2 for protocol deviations, which may lead to the exclusion of a subject from the Per Protocol population)

A listing of important protocol deviations will be produced. Subjects excluded from Per Protocol can be found in the listing of subjects excluded from any populations (see below).

Inclusion and exclusion criteria deviations will be summarized and listed.

6.2.3. Populations Analyzed

The number of subjects who were randomized into the study, the number of subjects within each analysis population (ITT, Per Protocol, Completers, Safety and PK) will be summarized for each treatment group and overall. A by-subject listing showing inclusion within each study population and a listing of subjects excluded from any populations will be produced.

The number and percentage of subjects will be summarized by country and by center within each country for each treatment group and overall.

6.2.4. Demography

Demographic and baseline data will include age, gender, ethnicity, race, diabetes, baseline height, baseline weight, baseline body mass index (BMI), prior ESA dose (stratification factor, Low ESA dose: <100 IU/kg/week epoetin OR <0.5 µg/kg/week darbepoetin OR <0.6 µg/kg/week methoxy PEG-epoetin beta vs. High ESA dose: ≥100 IU/kg/week epoetin OR ≥0.5 µg/kg/week darbepoetin OR ≥0.6 µg/kg/week methoxy PEG-epoetin beta), type of ESA, standardized prior rhEPO Dose (IU/kg/Week, including epoetin, darbepoetin, and Mircera), baseline Hgb, baseline ferritin, baseline absolute reticulocyte count, baseline iron-based phosphate binder (ferric citrate and sucroferric oxyhydroxide), and baseline pre-dose plasma EPO. In addition, the following data will be categorized and summarized for each treatment group and overall:

- Age (<65, ≥65 years)
- Baseline Hgb (< 10, ≥ 10 g/dL)
- Baseline Weight (≤Median, > Median kg)
- Baseline BMI (<27, ≥27 kg/m²)
- Race (White, African American, Asian, Other)
- Standardized Prior rhEPO (≤xx.xx, >xx.xx and < xx.xx, ≥xx.xx) (Tertile)
- Diabetes (Yes, No)
- Iron-based Phosphate Binders (Yes, No)
- Baseline Absolute Reticulocyte Count (≤ Median, >Median TI/L)

All the above demographic and baseline data will be summarized by treatment group and overall for the Safety, ITT and All Randomized populations.

A by-subject listing of demographic and baseline characteristics will also be produced.

Summaries of race and racial combinations and race and racial combination details will be produced for each treatment group and overall. A listing of race and racial combination details by subject will also be produced.

6.2.5. Medical Conditions and Concomitant Medications

The number and percentage of subjects with each past and current medical condition will be reported for each treatment group and overall. Past conditions are those reported as ‘past’ and current conditions are those reported as ‘current’ at screening. Past and current conditions will be reported separately. Medical conditions will be coded using the Medical Dictionary for Regulatory Activities (current MedDRA version at the time of DBR) and reported by system organ class (SOC) and preferred term.

Summaries of family history of cardiovascular risk, and substance use history will be provided by treatment group and overall.

Furthermore, summaries of baseline hemodialysis (mode of dialysis) will be produced by treatment group and overall.

By-subject listings of data for past and current medical conditions, cardiovascular risk assessments, and history of substance use will be produced separately. In addition, a listing of hemodialysis will be provided.

For reporting purposes, medications will be classified as prior, concomitant, and/or post-treatment using the associated start and stop dates recorded in the eCRF and relative to the first and last dose dates of IP (see Section 11.4.2.3). Medications will be coded using the GSK Drug coding dictionary (current version at the time of DBR).

Concomitant medications will be summarised by GSK-Drug Anatomical Therapeutic Chemical (ATC) classification level 1 (body system) and ingredient. Drugs that are composed of a combination of ingredients will be displayed according to the ATC classifications of the ingredients, not of the combination.

A summary of the number and percentage of subjects receiving concomitant medications will also be displayed using a method that presents multi-ingredient medications according to their combination ATC classification rather than the classifications of the ingredients. This display will also include single-ingredient medications. Multi-ingredient medications will be labelled according to the sum of their ingredients, e.g., “TYLENOL Cold and Flu” would appear as “CHLORPHENAMINE MALEATE + DEXTROMETHORPHAN HYDROBROMIDE + PARACETAMOL + PSEUDOEPHEDRINE HYDROCHLORIDE” under the ATC headings for “Nervous System” and “Respiratory System” (the combination’s ATC classifications). A multi-ingredient drug’s component ingredients will not be summarized separately.

A listing of all medications taken by subjects, including any which are only prior or post-treatment, will be produced. The relationship between ATC level 1, ingredients and verbatim text for all medications in the study will be listed.

A summary of prior erythropoiesis-stimulating agents taken in the 12 weeks prior to randomization will be produced. In addition, if any subject takes erythropoiesis-stimulating agents during the 29-day treatment period of the study (prohibited medication for all subjects between Day 1 and Day 29) this will be tabulated by treatment group. A bar chart showing the proportions of subjects taking different prior erythropoiesis-stimulating agents will be provided. A histogram of prior standardized rhEPO dose will also be produced.

A listing of prior erythropoiesis-stimulating agents and a listing of all (prior, concomitant, and post-treatment) erythropoiesis-stimulating agents will be provided.

Pre-therapy and on-therapy average iron dose (separately for oral and IV) by treatment group will be summarized. In addition, a table showing the number of subjects (i) using IV iron at Study Treatment Start and Final visit, (ii) stopping IV iron on-therapy and (iii) starting IV iron after treatment start will be produced for the Safety and Completers population. All iron therapy data taken during the study will be listed.

A summary and a listing of any blood products or blood supportive care products taken during the study will be produced by treatment group.

6.2.6. Exposure and Treatment Compliance

The complete dosing experience will be listed for all subjects. The total duration of exposure (number of days on study drug), average three times a week dose and cumulative dose will be summarized by treatment group and Dapro total.

The average three times a week dose (the cumulative actual dose divided by the expected number of doses during the treatment period) is calculated for each subject first and the summary statistics for each treatment group and for Dapro Total are calculated based on the subject average TIW dose.

$$\text{Cumulative actual dose} = \sum_{\text{bottle}=1}^3 \left(\frac{\text{No. of tablets taken from each bottle} *}{\text{tablet strength (mg/tablet)}} \right)$$

Note: The tablet strengths are 5 mg or 25 mg for subjects randomized to dapro arms, and 0 mg for subjects randomized to placebo arm (unless the subject received daprodustat by mistake during the study).

For subjects who completed the 29-day treatment period, the expected number of doses during the treatment period is 13. For subjects who permanently discontinued the study treatment and/or withdrew from the study, the expected number of doses during the treatment period will be calculated in the same way as the calculation of the expected cumulative number of tablets for each bottle described below for compliance calculation.

For each subject “Days on study drug” will be calculated as Last Dose Date – First Dose Date +1.

A summary and a listing of study medication compliance will be produced by treatment group.

For each bottle, the compliance will be calculated for the whole study treatment period as the percentage of the cumulative number of tablets taken $[100 * (\text{cumulative number of tablets taken}) / (\text{expected cumulative number of tablets for the subject's treatment duration})]$. For subjects who completed the 29-day treatment period, the expected cumulative number of tablets should be 13. For subjects who were permanently discontinued study treatment or early withdrew from the study, following algorithm will be used to calculate the “expected cumulative number of tablets” taken from each bottle during the treatment period:

1. Determine the expected “dose day”, where “dose day” is defined as days since the first dose date. (i.e. dosing date – first dose date +1)
 - a. For a subject who receives dialysis 3-5 times per week and starts dosing on Monday or Tuesday, the expected dose days are: 1, 3, 5, 8, 10, 12, 15, 17, 19, 22, 24, 26, and 29.
 - b. For a subject who receives dialysis 3-5 times per week and starts dosing on Wednesday or Thursday, the expected dose days are: 1, 3, 6, 8, 10, 13, 15, 17, 20, 22, 24, 27, and 29.
 - c. For a subject who receives dialysis 3-5 times per week and starts dosing on Friday or Saturday, the expected dose days are: 1, 4, 6, 8, 11, 13, 15, 18, 20, 22, 25, 27, and 29.
2. Determine the “expected cumulative number of tablets” by comparing the last dose day (last dose date – first dose date +1) with the expected dose days. For example, for a subject who received dialysis 3 times per week and started dosing on Wednesday, if the subject’s last dose day is day 7, then the expected cumulative number of tablets taken from a bottle should be 3 (because the last dose was administered before the fourth dose day); if the subject’s last dose day is day 8, then the expected cumulative number of tablets taken from a bottle should be 4 (because the last dose was administered on the fourth dose day).
3. For all other situations which is not covered in step “1” (i.e. a subject who does not receive dialysis 3-5 times per week and/or does not start dosing on Monday – Saturday), the following formula will be used to estimate the “expected cumulative number of tablets” taken from each bottle during the treatment period:

$$\text{Expected cumulative number of tablets} = \text{round}((i - 1) * 3/7, 1) + 1$$

Where “i” is the “last dose day”.

Overall compliance for a subject is categorized as follows: >0% and <80% if compliance for at least one bottle is <80%, 80% to 120% if compliance for all three bottles is between 80% and 120%, and >120% otherwise.

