6. STUDY TREATMENT

6.1. Investigational Product and Other Study Treatment

The term 'study treatment' is used throughout the protocol to describe any combination of products received by the subject as per the protocol design. Study treatment may therefore refer to the individual study treatments or the combination of those study treatments.

	Study Treatment				
Product name:	GSK1278863	Placebo			
Dosage form:	Tablet	Tablet			
Unit dose	5 mg and 25 mg tablet	0 mg			
strength(s)/Dosage	strengths/10 mg, 15 mg, 25 mg,	_			
level(s):	30 mg dosage levels				
Route of Administration:	Oral	Oral			
Physical description:	A round, biconvex, 10 mm white	A round, biconvex, 10 mm white film			
	film coated tablet.	coated tablet.			

All eligible subjects will discontinue their current ESA therapy and will be randomized to receive either GSK1278863 or matching placebo on a dialysis day. This should be timed such that randomization (Day 1) occurs on the date that would have been the next scheduled dose of ESA (or as close as practicable). In addition, for subjects with a three times weekly dialysis schedule, Day 1 must not occur on the first dialysis session of the week (e.g., if Monday-Wednesday-Friday schedule, the study visit cannot be on Monday). For subjects with a four to five times weekly dialysis schedule, Day 1 can be on any hemodialysis session of the week. Examples of switching are provided in the SRM.

To maintain the blind, subjects will have study treatment dispensed from three bottles of study medication. This combination of tablets will provide the appropriate dose of study medication, and will include a combination of tablet strengths, active and placebo, to correspond to the appropriate dose.

Subjects will be dispensed one tablet from each bottle (all subjects will take three tablets in total) and take with a glass of water on a dialysis day, and this should be prior to dialysis; however, on Day 1 it is acceptable for the subject to take study medication after dialysis. All study medication should be taken in the clinic **EXCEPT** prior to the PK day (Day 15 study visit), or on other days only if the Investigator and GSK Medical Monitor agree that it will not interfere with the study procedures or affect the subject's compliance

with the protocol. The study site must ensure that the date and time the subject took each dose of study treatment is documented.

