$$\text{Standardized rhEPO IV dose (IU/kg)} = 161/113 * (\text{epoetin SC dose (units)}) / (\text{weight (kg)})$$

- 4) For subjects taking Mircera (IV), their dose will be converted as follows:

$$\text{Standardized rhEPO IV dose (IU/kg)} = (\text{Mircera dose (mcg)}) / (1.2 * \text{weight (kg)})$$

2. If all the records of prior ESA use during the 12-week period prior to randomization have dose frequency = “ONCE”, then:

$$\text{Standardized rhEPO IV dose (IU/kg/week)} = \text{Sum of Standardized rhEPO IV dose (s) (IU/kg)} / 12$$

Note: This includes the situations when either a subject has only one prior ESA use record with dose frequency = “ONCE” or a subject has more than one prior ESA use records and all of them have dose frequency = “ONCE”.

3. If, in addition to the prior ESA use record(s) with dose frequency = “ONCE”, a subject has other ESA use record(s) with different dose frequency during the 12-week period prior to randomization, then the Standardized rhEPO IV doses calculated from Step 1 in terms of epoetin IV (IU/kg) will contribute directly (without considering “Gap Factor”) to the total Cumulative Dose derived in Step 6 of calculation of average weekly dose.

Extent of Exposure

- Number of days of exposure to study drug will be calculated based on the formula:
Duration of Exposure in Days = Treatment Stop Date – Treatment Start Date + 1
- Subjects who were randomized but did not report a treatment start date will be categorised as having zero days of exposure.
- The cumulative dose will be based on the formula:
Cumulative Dose = Sum (Each dose taken recorded in the eCRF, including the dose taken on or prior to PK day Day 15 study visit)

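### The SAP's tablet-strength note omits the 0 mg tablets that three of the four daprodustat arms must contain, so the stated input to cumulative dose is wrong for those arms

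*SAP*

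**What the plan says.** Protocol 6.1 lists active tablets as "5 mg and 25 mg tablet" strengths and the placebo tablet as 0 mg. To keep the blind, each subject takes one tablet from each of three bottles, so "all subjects will take three tablets in total". The set of bottles "will include a combination of tablet strengths, active and placebo, to correspond to the appropriate dose".

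SAP 2.3 gives the arms as "one of four three-times weekly doses (10 mg, 15 mg, 25 mg, or 30 mg of GSK1278863), or placebo".

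SAP 6.2.6 defines cumulative actual dose as the sum over three bottles of tablets taken times strength in mg per tablet. The note beneath it reads: "The tablet strengths are 5 mg or 25 mg for subjects randomized to dapro arms, and 0 mg for subjects randomized to placebo arm". The only exception it makes is for a placebo subject who received daprodustat by mistake. The average three-times-weekly dose is this cumulative dose divided by the expected number of doses; for completers, "the expected number of doses during the treatment period is 13".

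SAP 11.6.2, under Extent of Exposure, defines the quantity a second time: "Cumulative Dose = Sum (Each dose taken recorded in the eCRF", with the Day 15 dose included. This version uses no tablet strength.

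**The concern.** The note fixes strength by randomized arm: 0 mg belongs to placebo, and 5 or 25 mg to daprodustat. Protocol 6.1 fixes it by bottle and puts placebo tablets into active regimens. Both cannot hold for an arm whose dose needs a placebo tablet.

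Under SAP 3.2 the contract research organization programs everything except the dose-response analyses, so the note is the instruction its programmers have for this derivation. Followed literally, it would misstate cumulative dose, which Protocol 9.4.3.1 promises, and the average three-times-weekly dose, which the SAP adds.

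The strength assigned to each bottle matters most for dosing errors. SAP 11.1.2 anticipates a subject who takes all three tablets from a single bottle. In the 30 mg arm that would be 75, 15 or 0 mg, depending on whether the bottle holds 25, 5 or 0 mg tablets. Only the true content of each bottle recovers the dose actually taken.

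**Working it through.** **Inputs.** Three tablets per dose, one per bottle; active strengths 5 and 25 mg; placebo tablet 0 mg (all Protocol 6.1). Doses of 10, 15, 25 and 30 mg (SAP 2.3). Expected doses for a completer: 13 (SAP 6.2.6; each of the three dose-day lists in that section also has 13 entries).

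**Step 1: what each dose must consist of.** The documents do not list bottle contents by arm, but the arithmetic leaves one solution for each dose when strengths are 0, 5 and 25 mg:

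- 10 = 5 + 5 + 0
- 15 = 5 + 5 + 5
- 25 = 25 + 0 + 0
- 30 = 25 + 5 + 0

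Three of the four active arms therefore contain at least one placebo tablet.

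**Step 2: what the note's strengths allow.** With 5 and 25 mg only:

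- 5 + 5 + 5 = 15
- 25 + 5 + 5 = 35
- 25 + 25 + 5 = 55
- 25 + 25 + 25 = 75

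Only the 15 mg arm can reach its assigned dose.

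**Step 3: the SAP formula with actual bottle strengths.** Cumulative dose = 13 × (sum of the three strengths): 13 × 10 = 130, 13 × 15 = 195, 13 × 25 = 325 and 13 × 30 = 390 mg. Dividing by 13 returns 10, 15, 25 and 30 mg. The formula works.

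**Step 4: the same formula under a literal reading of the note.** Each placebo tablet now needs a nonzero value. The note allows 5 or 25 mg and does not say which, so both are shown as assumptions, for a completer with all 13 doses.

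| Arm | Actual per dose / total | Placebo tablets at 5 mg | Placebo tablets at 25 mg |
|---|---|---|---|
| 10 mg | 10 / 130 mg | 15 / 195 mg (+50%) | 35 / 455 mg (+250%) |
| 15 mg | 15 / 195 mg | 15 / 195 mg (0%) | 15 / 195 mg (0%) |
| 25 mg | 25 / 325 mg | 35 / 455 mg (+40%) | 75 / 975 mg (+200%) |
| 30 mg | 30 / 390 mg | 35 / 455 mg (+17%) | 55 / 715 mg (+83%) |

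For example, in the 30 mg arm, 455/390 − 1 = 0.167 and 715/390 − 1 = 0.833.

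With equal arms, the Dapro Total mean per dose is (10 + 15 + 25 + 30)/4 = 20 mg. It becomes (15 + 15 + 35 + 35)/4 = 25 mg (+25%) at 5 mg, and (35 + 15 + 75 + 55)/4 = 45 mg (+125%) at 25 mg.

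**Step 5: what uses this quantity.** Cumulative dose feeds the exposure summary (SAP Table 1.31) and the average three-times-weekly dose. Compliance in SAP 6.2.6 counts tablets per bottle, not milligrams. The Emax model in SAP 7.1.2 uses dose level, not cumulative dose. Neither is touched.

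**The case against.** The strongest reply is that the formula is right and the note is shorthand for the active strengths. The formula works bottle by bottle in mg per tablet, Protocol 6.1 gives the placebo tablet as 0 mg, and the note's own exception suggests that strength follows what was taken. A programmer who uses real bottle contents gets the right totals, as does one who uses SAP 11.6.2. An average of 35 mg in a 25 mg arm would also be noticed.

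Most of this stands, and it limits the point. It does not rescue the note, which assigns 0 mg by arm and considers an exception without covering the routine case of a placebo bottle in an active arm. SAP 11.6.2 does not override it either: 6.2.6 builds the average dose on the tablet formula, and neither section says which definition governs.

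A reader might infer more than the documents support:

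- **That exposure will be overstated by 17% to 50%.** This requires counting each placebo tablet at 5 mg, which no text says. It is one end of a range; true bottle strengths give no error.
- **That the 10 and 15 mg arms, and the 25 and 30 mg arms, would look identical.** This happens only under the 5 mg assumption. At 25 mg the four arms come out at 35, 15, 75 and 55 mg, all different.
- **That the protocol promises the average three-times-weekly dose.** Protocol 9.4.3.1 promises duration, final dose and cumulative dose. The average comes from the SAP.
- **That the two definitions of cumulative dose conflict.** With actual strengths and complete records they give the same total. The gap is that the SAP does not tie them together.

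**Conclusion.** The note in SAP 6.2.6 is wrong as written for the 10, 25 and 30 mg arms, because the strengths it states cannot produce those doses from three tablets. This follows from the two documents and needs no outside figure. The cumulative-dose formula is not at fault.

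The numerical consequence is conditional. It is zero if actual bottle strengths are used. Under a literal reading it is +50%, +40% and +17% for the 10, 25 and 30 mg arms with placebo tablets counted at 5 mg, and +250%, +200% and +83% at 25 mg. These figures assume a completer with 13 full doses. The 15 mg arm is correct throughout.

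Severity is low. Two descriptive exposure outputs are at risk, and the primary dose-response analysis and tablet-count compliance are not.

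**What to change.** Reword the note in SAP 6.2.6 to say that the strength of each bottle is 0, 5 or 25 mg according to its actual content, and that daprodustat arms include 0 mg (placebo) tablets where needed to make up three tablets. A short list of bottle contents by arm would remove any doubt. State in both 6.2.6 and 11.6.2 that this bottle-level calculation is the one definition of cumulative dose.

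The cost is a sentence or two in the SAP, with no change to design, data collection or inference. Protocol 6.6 already has the bottle number recorded for doses given in the clinic. The documents do not say where the contents of each numbered bottle are held, so the sponsor should name that source.
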